12.2.1 Interim analyses

No interim analysis will be scheduled

12.3 Determination of sample size

According to our previous research¹⁹ and other available studies on the subject²⁰ we have assumed post-procedural cTnI to be approximately 0.10ng/mL in the RPC group (0.08ng/mL for the ticagrelor group and 0.12 for the clopidogrel group) and approximately 0.19ng/mL for the control group (0.14ng/mL for the ticagrelor group and 0.24 for the clopidogrel group), with a standard deviation of 0.20 for both groups. According to our previous experience the correlation coefficient between preprocedural and postprocedural cTnI is approximately 0.7. Based on previously published methods,^{28,29} we have estimated a sample size of 152 patients (38 patients for each group) to achieve a statistical power of 80% with $\alpha=0.05$, incorporating a dropout rate of 15% (pci failure, revoked consent, etc.)

Statistical analyses have been performed using IBM SPSS Statistics v21, (IBM Corporation), and Power Analysis v1.4 (A&X Analytics).

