1.2 Research hypothesis

We will study the effect of ticagrelor on the reduction of PMI and the incidence of post-PCI MI with the use of RIPC. Our primary research hypothesis is that treatment with ticagrelor will potentiate the effects of RIPC and, therefore, reduce PMI, as assessed by post-procedural troponin release.

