1.4 Benefit/risk and ethical assessment

Peri-procedural cardiac troponin elevation has been associated with new irreversible myocardial injury and several studies have reported that peri-procedural injury is associated with worst prognosis. According to the available evidence, the prognostic significance of PMI is more pronounced when pre-procedural troponin is increased, i.e. in the setting of acute coronary syndromes. Data from the Cardiac Remote Ischemic Preconditioning in Coronary Stenting (CRISP Stent) study support that implementation of a RIPC protocol during PCI may reduce major adverse cardiovascular events during long-term follow-up and that post-procedural troponin I concentration associated with the development of major adverse cardiovascular events.²¹ If this protective effect is potentiated with treatment with ticagrelor, patients are expected to further benefit.

Ticagrelor has been shown to reduce significantly the rate of death from vascular causes, myocardial infarction, or stroke in patients with an acute coronary syndrome (ACS) with or without ST-segment elevation, compared to clopidogrel. These benefits were obtained without an increase in the rate of overall major bleeding but with an increase in the rate of non-procedure-related bleeding.²² Accordingly, treatment with ticagrelor in patients undergoing PCI for non ST-segment elevation ACS (NSTEMI-ACS) or ST-segment elevation MI (STEMI) has been approved by the European Medicines Agency (EMA) and carries a Class I level of evidence B recommendation from the European Society of Cardiology (ESC)²³

Even though ticagrelor has not received approval in patients with stable CAD, several clinical trials have assessed its pharmacodynamic and pharmacokinetic effects in comparison with clopidogrel in this patient population, proving superior efficacy in platelet inhibition with a safety profile consistent with previous studies.^{24,25,26,27}

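### The cell means in 12.3 assume RIPC lowers cTnI less on ticagrelor (0.06 ng/mL) than on clopidogrel (0.12), which does not fit the potentiation hypothesis in 1.2; 12.2 names no test of it

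*Combined protocol and SAP*

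**What the plan says.** Section 1.2 states: "Our primary research hypothesis is that treatment with ticagrelor will potentiate the effects of RIPC and, therefore, reduce PMI". Section 1.4 ties the expected benefit to the same idea: "If this protective effect is potentiated with treatment with ticagrelor, patients are expected to further benefit".

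Section 2.1 words the primary objective differently, as superiority of the ticagrelor-RIPC combination over clopidogrel with RIPC or over ticagrelor alone.

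Section 12.3 gives the planning values for post-procedural cTnI. Without RIPC they are "approximately 0.19ng/mL for the control group (0.14ng/mL for the ticagrelor group and 0.24 for the clopidogrel group"). For preconditioned patients the assumed means are 0.08 on ticagrelor and 0.12 on clopidogrel, averaging 0.10. The SD is taken as 0.20 throughout, and the assumption for the covariate is that "the correlation coefficient between preprocedural and postprocedural cTnI is approximately 0.7". From these it arrives at 152 patients, 38 per cell, for 80% power at a 5% type I error rate with 15% dropout. It does not say which comparison the power refers to.

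Section 12.2 specifies an ANCOVA of post-procedural cTnI, with no transformation mentioned, with the drug and RIPC as fixed factors and baseline cTnI as covariate. It names neither an interaction term nor a contrast that represents the hypothesis in 1.2.

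**The concern.** If ticagrelor potentiates RIPC, the fall in cTnI produced by RIPC should be larger on ticagrelor than on clopidogrel. In ng/mL the planning means say the opposite: the fall is half as large on ticagrelor.

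The hypothesis in 1.2 also runs two ideas together, that ticagrelor potentiates RIPC and that injury is therefore reduced. This makes it easy to take lower troponin on ticagrelor as evidence of potentiation. Under the planning means most of the drug effect comes from patients who were not preconditioned, so that inference would be wrong, and nothing in 12.2 separates the two ideas. At stake is the interpretation of the primary result, not the conduct of the trial or its data.

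**Working it through.** **Inputs.** All from 12.3 unless noted: means with RIPC 0.08 (ticagrelor) and 0.12 (clopidogrel); without RIPC 0.14 and 0.24; SD 0.20; pre/post correlation 0.7; power 80%; dropout 15%. Two-sided 5% is from 12.2. Four equal cells follow from the allocation in 3.1. Normal approximations are used throughout.

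**1. Reproducing 152.**
- Covariate-adjusted SD = 0.20 × √(1 − 0.7²) = 0.1428.
- Ticagrelor main effect: (0.12 + 0.24)/2 − (0.08 + 0.14)/2 = 0.18 − 0.11 = 0.07.
- n per arm = 2 × (1.96 + 0.8416)² × 0.1428² / 0.07² = 65.4, so 66 per arm and 132 evaluable.
- 132 × 1.15 = 151.8, so 152, an exact match. Dividing by 0.85 instead gives 156.
- The ticagrelor effect without RIPC, 0.24 − 0.14 = 0.10, gives 33 per cell and again 132, so the documents do not settle which of the two was used.
- The RIPC main effect (0.09) gives 80 evaluable. The two comparisons in 2.1 give 804 (difference 0.04) and 356 (difference 0.06). None of these leads to 152.

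**2. RIPC effect within each drug.**

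| | No RIPC | RIPC | Fall (ng/mL) | Relative fall |
|---|---|---|---|---|
| Clopidogrel | 0.24 | 0.12 | 0.12 | 50% |
| Ticagrelor | 0.14 | 0.08 | 0.06 | 43% |

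The interaction is 0.12 − 0.06 = 0.06 ng/mL against potentiation. Put another way, exact additivity would put the combination cell at 0.24 − 0.12 − 0.10 = 0.02. The plan assumes 0.08, and potentiation would need a value below 0.02.

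**3. Sensitivity to rounding.**
- *Absolute scale.* If each mean can move by 0.005, the fall on ticagrelor is at most 0.145 − 0.075 = 0.07 and on clopidogrel at least 0.235 − 0.125 = 0.11. The direction holds.
- *Ratio scale.* Values of 0.0755, 0.1245, 0.1445 and 0.2355 round to the printed means and keep the 0.10 and 0.19 averages. They give ratios of 0.0755/0.1445 = 0.522 and 0.1245/0.2355 = 0.529. The gap vanishes, so the ratio scale is no independent confirmation.

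**4. What the trial would show if the planning means were true.** After dropout 38 × 0.85 = 32.3 per cell remain.
- Ticagrelor main effect: power 79.5% (80.4% with 33 per cell).
- Interaction SE = √(4 × 0.1428² / 32.3) = 0.0503, and 0.06 / 0.0503 = 1.19. The estimate points against potentiation with probability Φ(1.19) = 0.88.
- The interaction is significant against potentiation with probability 22% and significant for it with probability 0.08%.
- The two estimates are close to independent in a balanced design, so a significant ticagrelor effect together with an interaction estimate against potentiation has probability of about 0.80 × 0.88 = 0.70.
- The drug effect is 0.10 without RIPC and 0.04 with it, so 0.10/0.14 = 71% of the sum comes from patients without RIPC.

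**5. Size needed to test an interaction of 0.06.** n per cell = 4 × 0.1428² × (1.96 + 0.8416)² / 0.06² = 177.9, so 178 per cell and 712 evaluable (819 with × 1.15, 838 with ÷ 0.85). With 33 evaluable per cell the two-sided power is 23%.

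**The case against.** The strongest reply is that 2.1, not 1.2, says what the trial is to demonstrate, and the means agree with 2.1: 0.08 is below both 0.12 and 0.14. Section 1.2 does not define potentiation or its scale, and read loosely it may mean only that troponin is lower when ticagrelor is added to RIPC. This stands in part. The means do not contradict every positive result, and the loose reading is possible. It is not the natural pharmacological reading, however, and if it is intended, 1.2 should say so.

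Three stronger inferences are tempting, and the documents do not support them:
- *That the trial was sized for potentiation.* Section 12.3 names no contrast, and the contrasts that reproduce 152 are not the interaction.
- *That the sponsor plans to report a ticagrelor main effect as potentiation.* No section says so. The gap is that 12.2 contains nothing to prevent it.
- *That the means show weakening on any scale.* On the ratio scale the difference of 50% against 43% is within rounding. Only the ng/mL result is firm.

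It may also be said that software often fits the interaction in a two-factor ANCOVA by default. That would not make it a prespecified test of 1.2, and the assumed direction would be unchanged.

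**Conclusion.** The inconsistency between 1.2 and 12.3 is real on the ng/mL scale: an assumed interaction of 0.06 against potentiation, in a plan whose primary hypothesis is potentiation. No other section reconciles the two. Under the planning means the ticagrelor main effect is significant about 80% of the time, while the interaction estimate points the wrong way for 1.2 about 88% of the time. A significant ticagrelor effect is therefore not support for 1.2.

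The probabilities rest on the plan's own means, SD, correlation and dropout, on a common SD in all four cells, and on a normal approximation. The direction rests on the means alone. The 152 itself is not shown to be miscalculated, and the objective in 2.1 is not contradicted. Severity: should-fix.

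**What to change.** Reconcile 1.2, 1.4, 2.1, 12.2 and 12.3.

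1. In 1.2 and 1.4, say that ticagrelor and RIPC are each expected to lower 24-hour cTnI and that the combination is expected to give the lowest level. This agrees with 2.1 and with the existing means.
2. In 12.3, state which contrast the 80% power refers to.
3. In 12.2, report the ticagrelor-by-RIPC interaction with its 95% CI on a stated scale. Allow a claim of potentiation only if the interval excludes zero in that direction. A rule based on the point estimate alone would be met about half the time with no true interaction.

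This costs wording and one extra reported estimate, with no additional patients or data. The downside is a more modest claim.

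If potentiation is kept as the primary hypothesis, 12.3 must use means in that direction and state the power that 152 patients give for the interaction: about 23% for an interaction of 0.06, against about 712 evaluable patients for 80%. Changing the combination mean alone would not be enough. With the other three means kept, an interaction of 0.06 towards potentiation would put that cell at 0.02 − 0.06 = −0.04 ng/mL, which is impossible.

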2. STUDY OBJECTIVES

2.1 Primary objective

The primary objective of this study is to demonstrate superior efficacy of a combination of ticagrelor and RIPC in the reduction of PMI compared to a clopidogrel-RIPC combination or ticagrelor alone, by evaluating post-procedural cardiac Troponin I (cTnI) levels, defined as cTnI at 24 hours post-PCI.

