12.2 Methods of statistical analyses

The efficacy analysis will be performed in the population of subjects valid for safety analysis.

The statistical assessment of the primary outcome measure (post-procedural cTnI) will be performed using ANCOVA (analysis of covariance), with post-procedural cTnI as a dependent variable, -ticagrelor/clopidogrel treatment and –RIPC/no RIPC as fixed factors and pre-procedural cTnI as a covariate. If not mentioned otherwise, all statistical tests will be performed tow-sided with a type I error rate of 5% and 95% confidence intervals (two-sided) will be given.

The statistical assessment of the secondary outcome measures (pain score, and ST-segment deviation) will be performed using ANOVA (analysis of variance). The ANOVA tests the null hypothesis that samples in two or more groups are drawn from populations with the same mean values. If the ANOVA test is statistically significant, pairwise comparison of subgroups will be performed with the Tukey-Kramer test. If not mentioned otherwise, all statistical tests will be performed tow-sided with a type I error rate of 5% and 95% confidence intervals (two-sided) will be given.

The safety analysis will be performed in the population of subjects valid for safety analysis.

The incidence of the composite of major and non-major bleeding according to the TIMI criteria and the incidence of major bleeding will be tabulated and further analyzed using Fisher's exact test. Fisher's exact test is a significance test for a 2x2 table. This test evaluates all distribution probabilities for a 2 x 2 table and produces an exact probability for a given set of observed frequencies. The null hypothesis is that the row and column variables are unrelated, or that there is no difference in the respective proportions. If not mentioned otherwise, all statistical tests will be performed two-sided with a type I error rate of 5% and 95% confidence intervals (two-sided) will be given.

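### The stated 80% power does not apply to the primary objective, whose two named comparisons have about 20% and 39% power on the plan's own assumptions

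*Combined protocol and SAP*

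**What the plan says.** Section 2.1 sets the aim to "demonstrate superior efficacy of a combination of ticagrelor and RIPC in the reduction of PMI compared to a clopidogrel-RIPC combination or ticagrelor alone", measured by cTnI at 24 hours after PCI.

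Section 12.3 gives a planning mean for each cell. With RIPC these are "0.08ng/mL for the ticagrelor group and 0.12 for the clopidogrel group"; without RIPC they are "0.14ng/mL for the ticagrelor group and 0.24 for the clopidogrel group". It adds "with a standard deviation of 0.20 for both groups" and states that "the correlation coefficient between preprocedural and postprocedural cTnI is approximately 0.7". It concludes that "we have estimated a sample size of 152 patients (38 patients for each group) to achieve a statistical power of 80" per cent at α = 0.05, with 15% dropout included. It does not say which comparison has this power.

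Section 12.2 plans an ANCOVA of post-procedural cTnI with drug and RIPC as fixed factors and pre-procedural cTnI as covariate. It names no pairwise contrast and no interaction for this outcome. On the error rate it says that "all statistical tests will be performed tow-sided with a type I error rate of 5" per cent.

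**The concern.** A reader will take a single, unlabelled power figure as the power of the primary objective. That objective names two comparisons between single cells, each using half of the patients, and the planned differences (0.04 and 0.06 ng/mL) are small against an SD of 0.20. They are also smaller than the other contrasts available in the design.

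If the 80% belongs to some other contrast, the trial is presented as likely to meet an objective that it would more likely than not miss, even if every assumption were true. A null result could then be read as evidence against the combination. A significant main effect could be reported as proof of it.

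**Working it through.** **Inputs (Sections 12.2 and 12.3).** Cell means in ng/mL: ticagrelor + RIPC 0.08, clopidogrel + RIPC 0.12, ticagrelor alone 0.14, clopidogrel alone 0.24. SD 0.20, taken as common to all four cells. Correlation r = 0.7. Two-sided α = 0.05. 38 enrolled per cell. Dropout 15%.

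**Residual SD after covariate adjustment:** 0.20 × √(1 − 0.7²) = 0.20 × √0.51 = 0.1428.

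**Reproducing the plan's figure.** The ANCOVA sample size per compared group is n = 2 × (1.96 + 0.84)² × (0.20/d)² × 0.51.

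- Ticagrelor v clopidogrel without RIPC, d = 0.24 − 0.14 = 0.10: n = 32.0 per cell. Dividing by 0.85 gives 37.7, so 38 per cell and 152 in total.
- Ticagrelor main effect, d = (0.12 + 0.24)/2 − (0.08 + 0.14)/2 = 0.18 − 0.11 = 0.07: n = 65.4 per drug, so 33 per cell. 132 × 1.15 = 151.8, so 152 in total.

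Both routes reach 152. Neither contrast is named in Section 2.1.

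**Power of each comparison.** Completers per cell: 38 × 0.85 = 32.3, taken as 32. Power is from the noncentral t distribution with 4 × 32 − 5 = 123 df. Standard errors:

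- pairwise: 0.1428 × √(2/32) = 0.0357
- main effect: 0.1428 × √(4/128) = 0.0252
- interaction: 0.1428 × √(4/32) = 0.0505

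| Comparison | Difference | Difference/SE | Power, 32 per cell | Power, 38 per cell (no dropout) |
|---|---|---|---|---|
| Ticagrelor + RIPC v clopidogrel + RIPC (Section 2.1) | 0.04 | 1.12 | 19.9% | 22.8% |
| Ticagrelor + RIPC v ticagrelor alone (Section 2.1) | 0.06 | 1.68 | 38.5% | 44.4% |
| Ticagrelor v clopidogrel, no RIPC | 0.10 | 2.80 | 79.4% | 85.8% |
| Ticagrelor main effect | 0.07 | 2.77 | 78.5% | 85.1% |
| RIPC main effect | 0.09 | 3.56 | 94.3% | 97.1% |
| Interaction | 0.06 | 1.19 | 21.8% | 25.1% |

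**The two Section 2.1 comparisons together** (simulated, with the shared ticagrelor + RIPC cell and no multiplicity adjustment): both significant, about 13%; at least one significant, about 45%. With no dropout these become about 17% and 51%.

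**What 80% power would need.** The same formula gives 200.1 completers per cell for d = 0.04 and 89.0 for d = 0.06. Conversely, with 32 per cell the pairwise difference detectable at 80% is about 0.10 ng/mL.

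**The case against.** The strongest reply is that Section 12.2 plans a two-factor ANCOVA and names no pairwise contrast. Read that way, the primary tests are the main effects, and the ticagrelor main effect has 78.5% power, or 79.8% with 33 completers per cell. On that reading the 80% belongs to the planned test, and the fault is a mismatch between Sections 2.1 and 12.2.

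The mismatch is real, but it does not rescue the power statement. The planned means are not additive: the drug effect is 0.12 − 0.08 = 0.04 with RIPC and 0.24 − 0.14 = 0.10 without. A main effect of 0.07 is the average of the two and comes mostly from patients without RIPC. It would not show that the combination beats clopidogrel plus RIPC.

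Three further points qualify the finding.

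- **The word "or".** If success on either comparison is enough, power is about 45%, close to even. With a Bonferroni adjustment it is about 33%. Neither is near 80%.
- **The sponsor's basis is inferred.** Section 12.3 names no contrast, and the methods it cites are not available here. Which route gives 152 also depends on how dropout is applied: for the main effect, 32.7/0.85 = 38.5 would round to 39 per cell, or 156. Two other calculations come near 80%, the RIPC main effect without covariate or dropout (79.2%) and the four-group F test without covariate (79.5%). Each ignores a stated input, and neither tests the Section 2.1 comparisons.
- **More lenient settings.** The most favourable variant tried for either named comparison (one-sided, no dropout, difference 0.06) reaches 57%.

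**Conclusion.** Section 12.3 is wrong as written if read, as it will be, as the power of the primary objective. On the plan's own means, SD, correlation, two-sided 5% level and 15% dropout, the two comparisons in Section 2.1 have about 20% and 39% power, with about 13% for both and 45% for at least one. These figures assume a common SD in all four cells and no multiplicity adjustment; an adjustment would lower the chance of at least one significant result. The conclusion does not depend on which contrast the sponsor used to reach 152.

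The hypothesis in Section 1.2, that ticagrelor potentiates RIPC, is no better served. The interaction has about 22% power, and the planned RIPC effect is smaller under ticagrelor (0.06) than under clopidogrel (0.12).

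**What to change.** Keep 152 patients and rewrite the power statement in Section 12.3 to say:

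- which comparison the sample size was calculated for, as confirmed by the sponsor;
- that, under the stated assumptions with 64 v 64 completers, the ticagrelor main effect of 0.07 ng/mL has about 79% power;
- that the two Section 2.1 comparisons have about 20% and 39% power with 32 v 32 completers;
- that the smallest pairwise difference detectable with 80% power is about 0.10 ng/mL.

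This costs a wording change and a less favourable stated power. It needs no added patients or procedures.

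If the sponsor wants a primary claim with about 80% power at this size, it could name the ticagrelor main effect as primary in Section 2.1 and report the combination contrasts as secondary estimates with 95% confidence intervals, defined in Section 12.2. That is a separate choice: it changes the research question and needs a protocol amendment with ethics approval. Powering the Section 2.1 comparisons instead would take far more patients. Allowing for dropout, 89/0.85 gives 105 per cell (420 in total) for the 0.06 difference, and 201/0.85 gives 237 per cell (948 in total) for the 0.04 difference.

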13. IMPORTANT MEDICAL PROCEDURES TO BE FOLLOWED BY THE INVESTIGATOR

13.1 Overdose

There is currently no known antidote to reverse the effects of ticagrelor, and ticagrelor is not expected to be dialyzable. Treatment of overdose should follow local standard medical practice.

The expected effect of excessive ticagrelor dosing is prolonged duration of bleeding risk associated with platelet inhibition. If bleeding occurs, appropriate supportive measures should be taken.

Ticagrelor is well tolerated in single doses up to 900 mg. Gastrointestinal toxicity was dose-limiting in a single ascending dose study. Other clinically meaningful adverse effects which may occur with overdose include dyspnoea and ventricular pauses.

In the event of overdose, observe for these potential adverse effects and consider electrocardiogram monitoring.

13.2 Pregnancy

All outcomes of pregnancy should be reported to AstraZeneca. The Investigator should substitute ticagrelor with an acceptable alternative, according to local practice, if dual antiplatelet treatment is considered appropriate.

